#### Post-menopause is defined as:

- Women who have had amenorrhea for >12 consecutive months (without another cause) and who have a documented serum follicle-stimulating hormone (FSH) level >35 mIU/mL.
- Women who have irregular menstrual periods and a documented serum FSH level >35 mIU/mL.
- Women who are taking hormone replacement therapy (HRT).

#### 4.1. Procedures

Statistical Analysis Plan Page 8 of 13

#### Recruitment:

Patients will be recruited from the outpatient clinic of the department of Internal Medicine of the Ziekenhuisgroep Twente. Prior to their visit to the outpatient clinic, patients will be invited to participate in the study by sending a letter.

#### Randomization and treatment allocation:

Treatment sequence of dapagliflozin and placebo will be randomized by the pharmacy unit of the University Medical Center Groningen. A computer-generated randomized code will be used. The pharmacy of the University Medical Center Groningen will store the randomization code.

#### Measurements:

Data collection will be performed at home using wearable devices and digital technologies. Data collection and measurements will be performed in each treatment period as indicated in Figure 1. The following devices will be used to measure bio-physical/anthropomorphic variables:

#### Body weight measurements:

Body weight will be measured by the Withings® Body+ (Withings, Issy-les Moulineux, France) device, which is a clinically validated advanced Wi-Fi smart scale that performs highly accurate bioelectrical impedance analysis (weight, body fat & water percentage, plus muscle & bone mass). Patients will be instructed to always weigh themselves under identical conditions. Preferably, weighing will take place in the morning, after showering or bathing, and with dry feet, but before breakfast. Patients will also be instructed to stand up straight and stand still.

#### Blood pressure measurements:

The Withings® BPM Connect device will be used to monitor blood pressure. This clinically validated Wi-Fi blood pressure monitor provides medically accurate blood pressure and heart rate measurements compliant with European medical device standards. The results are within the margin of acceptance defined by the internationally recognized evaluation standard of blood pressure monitors ANSI/AAMI/ISO 81060-2:2013, EN ISO 81060-2:2014, developed by the European Society of Hypertension, British Hypertension Society and Association for the Advancement of Medical Instrumentation/American Heart Association. Both of the Withings devices will be connected with a smartphone app in order to transfer the data to Selfcare platform. Prior to starting home blood pressure monitoring, patients will be instructed to measure their blood pressure in both arms to determine which arm should be used for future measurements. The arm that gives the higher systolic reading should be used for all future testing. Patients should place the cuff on their arm with the lower edge of the cuff approximately 2cm above the bend in their elbow. The center of the inflatable bladder should be positioned over the brachial artery on the arm's inferior surface. The forearm should be supported on a firm surface and should be at the level of the lower end of the breastbone. No tight or

Statistical Analysis Plan Page 9 of 13

restrictive clothing should be worn around the arm. Patients should be seated, remain silent and be at rest for a minimum of five minutes before taking a measurement and should not have smoked, eaten, drunk a caffeinated drink or undertaken physical activity within the past thirty minutes. Patients should also avoid measuring their blood pressure with. a full bladder. Measurements should be taken in silence when the patient is relaxed, with both feet flat on the floor and their back and arm supported. Many patients automatically cross their legs, which raises their blood pressure, so it is particularly important to emphasize the need for the patient to uncross their legs when taking their blood pressure. For each BP recording, three consecutive measurements are taken, at least 1 minute apart with the person seated. BP is recorded once daily.

Blood and urine will be sampled with dedicated devices:

#### • *Blood sampling:*

Capillary blood will be sampled using a BD Microtainer® Contact-Activated Lancet (Franklin Lakes, New Jersey, USA). Blood is collected with the Hem-Col® device, which is designed to collect capillary blood drawn with a finger prick. Hem-Col is a microtube containing an anticoagulant and a preservation buffer to enhance analyte stability in whole blood. The Hem-Col® device containing 17 USP/mL lithium heparin dissolved in 150 µL preservation fluid (Hem-Col, Labonovum, Limmen, the Netherlands) will be used. Hem-Col tubes have the size of regular blood collection tubes (13 x 75 mm) and are made of polyethylene, with a pierceable cap made of thermoplastic elastomers. All tubes contain a liquid barrier, the inner part serves as a liquid barrier by preventing loss of Hem-Col conservation fluid and the outer part is used as a scoop to collect blood from a finger prick. Hem-Col lithium heparin will be used for analyses of creatinine, C-reactive protein (CRP), lipid profile, HbA1c, uric acid and the N-terminal prohormone of brain natriuretic peptide (NT-proBNP). The Hem-Col device can be sent to the laboratory for analysis by regular post. Capillary blood sampled by BD Microtainer® Contact-Activated Lancet will also be used to determine fasting plasma glucose. If a patient already has an eligible glucose meter, this device can be used in order to determine fasting plasma glucose. In this case, patients have to manually enter their blood glucose results in Selfcare platform. If a patient does not already have a glucose meter, an Accu-Chek® Instant System (Roche Diagnostics, GmbH, Mannheim, Germany) device with appropriate test strips (Accu-Chek® Instant) will be provided during the randomization visit. The accuracy of the Accu-Chek® Instant System is guaranteed by the makers of the Accu-Chek products, fulfilling the requirements of the ISO 15197:2013/EN ISO 15197:2015. Once connected to Google fit, the meter automatically logs blood glucose results and wirelessly transfers them to Selfcare platform.

# First morning void urine collection: Urine will be collected with the PeeSpot® (Hessels+Grob, Apeldoorn, the Netherlands) device, which is a validated tool for collection and conservation of small amounts of urine. It consists of a urine absorption pad, a holder, a tube and a

Statistical Analysis Plan Page 10 of 13

lid. Patients can void over the absorption pad while placed in the holder. After voiding, the pad and holder are placed in the tube, closed with the lid and kept in the refrigerator until sending to the laboratory. By adding an inert hygroscopic polymer, the pad easily absorbs 1.2 mL urine and by adding various preservatives, urine is preservable for 4 days. After completing the urine collections, the PeeSpots are placed in a safety bag and sent to the central laboratory in an envelope for biological materials (PolyMed, DaklaPack, Europe). We will use the PeeSpot to determine the first morning void UACR. The PeeSpot has been validated for measurement of urinary albumin and creatinine.

#### • Treatment adherence:

Medication will be provided in standard medicine bottles with the MEMS® (Medication Electronic Monitoring System) Cap (AARDEX Ltd, Union City, CA, USA), which is a customizable medication package which records and stores up to 4,000 dosing events. The cap fits on standard medicine bottles and with integrated microcircuits, the child-resistant MEMS® Cap records the date and time whenever a patient opens a vial. The stored information can be transferred at any time through the MEMS® Reader to the adherence software for immediate analysis and interpretation.

#### • Laboratory measurements:

Dapagliflozin concentration measurements will be performed at the University Medical Center Groningen using liquid chromatography mass-spectrometry (LC-MS/MS) in capillary blood samples. First morning void UACR measurements will also be performed at the laboratory of the University Medical Center Groningen. Blood (creatinine, CRP, lipid profile, HbA1c, uric acid and NT-proBNP) measurements will be performed at the laboratory (Medlon BV) of the Ziekenhuisgroep Twente. Residual urine and blood plasma samples will be stored at the University Medical Center Groningen in the context of this study to allow for future exploratory biomarker analyses to further study the effects of dapagliflozin on type 2 diabetes, albuminuria and kidney function. Samples will be stored with the same patient number used in the study database. The samples are only accessible to the principal investigator and other delegated members of the study team. No biobank is made.

Statistical Analysis Plan Page 11 of 13

#### 5. Statistical analysis

Patients will be described with their demographical and medical data. Baseline characteristics will be presented as mean and standard deviation for parametric data and as median and 25th and 75th percentile for non-parametric data. Non-parametric data including 24-hour albuminuria and urinary albumin:creatinine ratio will be log-transformed for regression analyses and the reverse of the log will be presented in summaries and results.

#### 5.1. Analysis of primary and secondary study outcome

The change from baseline in UACR will be calculated using the values collected at day 5, 6 and 7 of each treatment and wash-out period. Because of the skewed distribution UACR will be log-transformed before analysis. The geometric mean of these 3 values (at baseline to end of treatment) will be calculated as log(UACRend/UACRbaseline) and the geometric mean change from baseline will be determined.

The study has two cycles of two treatment periods (dapagliflozin and placebo). For the calculation of response, the difference in log-transformed UACR change between dapagliflozin and placebo will be calculated during the first and second cycle. Patient level Bayesian analysis:

First, a Bayesian analysis will be conducted to calculate the posterior probability of dapagliflozin producing a clinically meaningful response on UACR within each individual patient relative to placebo for both treatment cycles combined. Thus for every patient, data of each cycle is combined and expressed in the form of a likelihood function with non-informative priors to calculate the posterior distribution. A clinically meaningful response on UACR is defined as the placebo subtracted percentage UACR change during the first and second cycle with different thresholds of 10%, 20% or 30% reduction in UACR. Population level Bayesian hierarchical analysis:

Subsequently, individual patient results on UACR will be combined to conduct a Bayesian hierarchical analysis to calculate the posterior probabilities of a clinically meaningful response at the population level (10%, 20%, and 30%). Therefore, responses on UACR from each patient will be aggregated into a sample mean and variance, assuming a normal distribution centred around the patient's true mean effect and variance. The Bayesian hierarchical model is defined as:

$$Y_{ij} \sim N(\alpha_i + \beta_i X_{ij}, \sigma_i).$$

Were  $Y_{ij}$  is the placebo subtracted UACR response for the  $i^{th}$  subject at time j and is described by  $x_{ij}$  ( $x_{ij}=1$  if treated with dapagliflozin; =0 if placebo treated). The subject specific intercept and slope were modelled as  $a_i \sim N(a_0, \tau_a^2)$  and  $\beta_i \sim N(\beta_0, \tau_\beta^2)$  respectively. Again, we used non-informative prior for  $a_0$ ,  $\beta_0$ ,  $\tau_a^2$ ,  $\tau_\beta^2$ ,  $\sigma_i$ .

We will repeat this analysis for the secondary outcomes such as blood pressure, body weight, and several clinical chemistry laboratory parameters, Similar to UACR, we will estimate the posterior probability of a clinically meaningful response and the overall treatment effect. clinically meaningful response as defined as:

• Blood pressure: reduction of 5 mmHg

Statistical Analysis Plan Page 12 of 13

• Body weight: reduction of 3kg

• Hba1c: reduction of 0.5%

• EGFR: reduction of 10% and 3 ml/min.

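### Neither Bayesian analysis in the SAP shares the within-patient variance between patients, so each individual posterior is less precise or less well calibrated than the same data allow

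*Combined protocol and SAP*

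**What the plan says.** SAP 5.1 sets out the data for one patient: "The study has two cycles of two treatment periods (dapagliflozin and placebo"), and "the difference in log-transformed UACR change between dapagliflozin and placebo will be calculated during the first and second cycle". Each change is formed "using the values collected at day 5, 6 and 7 of each treatment and wash-out period", with the three daily values reduced to a geometric mean.

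- **Patient-level analysis.** One posterior is formed per patient: "data of each cycle is combined and expressed in the form of a likelihood function with non-informative priors to calculate the posterior distribution". The output is the probability of a clinically meaningful response, "with different thresholds of 10%, 20% or 30% reduction in UACR". The text gives no likelihood family and no rule for the variance, and it brings in no data from other patients.
- **Population-level analysis.** Here "responses on UACR from each patient will be aggregated into a sample mean and variance, assuming a normal distribution" centred on the patient's true effect. The model has subject-specific intercepts and slopes drawn from common normal distributions, but the residual term is sigma_i, one per patient. The sentence that begins "Again, we used non-informative prior for" ends its list with sigma_i, so these variances are not tied together.

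The SAP repeats the approach for the secondary outcomes. It names no credible-interval level and no probability cut-off for calling a patient a responder.

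**The concern.** The primary objective is the individual response, and the trial's rationale is to separate true response from random variation. A patient's posterior probability depends as much on the variance attached to the effect as on the effect itself. Two differences give very poor information on a variance: an SD on 1 df lies between 0.06 and 1.96 times the truth (5th to 95th percentile), whereas pooling over 20 patients (20 df) narrows this to 0.74-1.25. Without sharing, two cycles that happen to agree can make one patient look certain, and two that happen to differ can make another look uninformative, for reasons unrelated to the drug.

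**Working it through.** **1. The plan's own figure.** SAP 3.2 gives more than 80% power for r = 0.6 with 20 patients at alpha 0.05. By Fisher's z, power = Phi(atanh(0.6) x sqrt(17) - 1.96) = Phi(0.693 x 4.123 - 1.96) = Phi(0.898) = 81.5% two-sided. It reproduces. The documents state no coverage figure; r = 0.6 is used below as the trial's own split of the variance of a cycle difference (60% between patients, 40% within).

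**2. Own variance, plugged in.** Two differences leave 1 df. The interval mean +/- 1.96 x s/sqrt(2) covers P(|t_1| < 1.96) = (2/pi) x arctan(1.96) = 70.0%. This needs normality and no assumed SD. If four period values are modelled (2 df), P(|t_2| < 1.96) = 81.1%. For a patient exactly on the threshold, a posterior probability above 0.95 occurs with P(t_1 > 1.645) = 17.4% instead of 5%.

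**3. Own variance, unknown.** With a prior proportional to 1/sigma the posterior is a t with 1 df. Coverage is 95%, but the multiplier is 12.71. Pooled over 20 patients it is t_20 = 2.086, and 12.71/2.086 = 6.1.

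As an illustration, assume a total SD of 0.4 log units for one cycle's response (not in the documents). The within-patient part is 0.4 x sqrt(0.4) = 0.253. Centre on ln(1 - 0.362) = -0.449, the 24-hour albumin excretion effect in protocol 6.3:
- 1 df, median s = 0.6745 x 0.253 = 0.171: half-width 12.706 x 0.171/sqrt(2) = 1.53, so -86% to +196%.
- Pooled: half-width 2.086 x 0.253/sqrt(2) = 0.373, so -56% to -7%.

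**4. Hierarchical model.** Simulated trials of 20 patients with two differences each, total SD 0.4 (assumed), r = 0.6 and diffuse priors; 60 trials, 1,200 patients per scenario:

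| True within-patient SDs | Coverage, own sigma_i | Coverage, common sigma |
|---|---|---|
| Equal | 89.6% | 94.3% |
| Unequal (log-SD 0.4, assumed) | 90.0% | 93.2% |

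Median widths with equal SDs are 0.74 and 0.63 (ratio 1.17). A repeat with 200 trials gave 89.8% and 94.1%, with widths 0.76 and 0.62 (ratio 1.23). So the intervals with own sigma_i are about 20% wider and still cover less.

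**5. Posterior probability above 0.95 of a reduction of at least 20%.** The threshold is ln(0.8) = -0.223. The within-patient SD of one cycle difference is assumed to be 0.25 or 0.45. A patient is counted when (-0.223 - mean)/(s/sqrt(2)) exceeds 1.645 (plug-in), 6.31 (t_1), or 1.725 with the pooled s (t_20). No shrinkage is applied.

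| True effect | Variance rule | SD 0.25 | SD 0.45 |
|---|---|---|---|
| None | Plug-in, 1 df | 2.3% | 6.4% |
| None | Unknown, 1 df | 0.6% | 1.8% |
| None | Pooled, 20 df | 0.2% | 1.0% |
| 36% reduction | Unknown, 1 df | 16% | 11% |
| 36% reduction | Pooled, 20 df | 34% | 17% |

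Plug-in gives about 6 to 11 times as many false calls as pooling.

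**The case against.** A reader might infer that each patient's posterior plugs in that patient's own sample variance, so that the trial's individual 95% intervals cover about 70%. The documents do not support that. The sentence on a sample mean and variance stands under the population-level heading. The patient-level text speaks of priors in the plural, and the later list gives sigma_i a prior, which points to an unknown variance rather than a plug-in. That route is calibrated: its calls are rare, not wrong. Nor does 70% carry to the hierarchical model, where shrinkage of the slopes brings coverage to about 90%.

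Three further points stand:
- The 95% level and the 0.95 cut-off are benchmarks chosen here. The SAP sets neither.
- The number of observations is ambiguous. The model codes dapagliflozin as 1 and placebo as 0, which suggests four period values, yet it describes the outcome as already placebo-subtracted.
- The frequentist mixed model and the heterogeneity regression in SAP 5.1 would, in their standard form, use one residual variance across patients. They do not, however, produce the posterior probabilities.

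A reader might also infer that these posteriors decide who is offered dapagliflozin after the study. The protocol (Summary, 8.6 and 11.4) ties the offer to response but names no posterior, threshold or probability.

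Finally, an unpooled analysis is a legitimate N=1 choice, and no variance model can make up for having two cycles. Even with pooling, a true 36% reduction passes 0.95 in only 17-34% of patients.

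**Conclusion.** The concern holds as a weakness in the stated model. SAP 5.1 assigns unpooled, non-informatively distributed sigma_i and shares no variance at patient level. For the hierarchical model the loss is moderate: about 89-90% coverage against about 94%, with intervals about 20% wider. This rests on normality, r = 0.6, two differences per patient, diffuse priors and an assumed total SD of 0.4. For the patient-level analysis the size depends on an unstated choice: 70% coverage if plugged in on 1 df, 81% on 2 df, or correct coverage with a multiplier 6.1 times the pooled one. The coverage figures and multipliers in that sentence need only normality; the false-call and detection rates depend on the assumed SDs of 0.25-0.45.

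**What to change.** In SAP 5.1, replace the independent non-informative sigma_i with one common within-patient sigma, or with sigma_i drawn from a shared hierarchical prior. Use the same pooled variance in the patient-level posterior. State whether the model takes two cycle differences or four period values per patient. Report each patient's probabilities at 10%, 20% and 30% from this model, apply the same rule to the secondary outcomes, and keep the unpooled analysis as a sensitivity analysis.

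The cost is SAP wording; no new data are needed. The downside is an assumption that log-scale variability is similar between patients. The day 5-7 samples allow a check on that, and with moderately unequal SDs the simulated coverage with a common sigma was still 93.2%, above the 90.0% of the model as written.

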#### Frequentist linear mixed effects analysis:

In addition to this Bayesian approach, we will also utilize a frequentist approach to determine the response on UACR during each period. To estimate this response a linear mixed effects model with random intercepts and random slopes for treatment will be used. Fixed effects include treatment sequence, and treatment cycle. Baseline log-transformed UACR may be added as covariate. Appropriate contrasts will be implemented to assess the placebo subtracted response during the first and second cycle and to correlate the placebo adjusted UACR responses to dapagliflozin (fitted on the log-scale) during the two treatment periods. The variance-covariance pattern of the mixed effects model is assumed to be unstructured. If the model does not converge less stringent models will be considered.

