#### 5.2. Sub group analysis:

The primary and secondary outcomes will be analyzed in the following subgroups by adding a subgroup parameter to the Bayesian hierarchical model as described above:

- 1. Age ( $\geq$  or < 65 years or median)
- 2. Gender (Male / Female)
- 3. Urinary albumin:creatinine ratio (≥ or < 300 mg/g (33.4 mg/mmol) or median)
- 4. eGFR ( $\geq$  or < 60 ml/min/1.73m^2 or median)
- 5. Systolic blood pressure (≥ or < 130 mmHg or median)
- 6. Body mass index ( $\geq$  or  $< 25 \text{ kg/m}^2$  or median)

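### SAP 5.1: the Bayesian hierarchical model regresses an already placebo-subtracted UACR response on a dapagliflozin/placebo indicator, so its treatment coefficient is not identified as written

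*Combined protocol and SAP*

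**What the plan says.** SAP 5.1 first forms the response: "the difference in log-transformed UACR change between dapagliflozin and placebo will be calculated during the first and second cycle". With two cycles, that gives two values per patient.

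For the population-level analysis, "responses on UACR from each patient will be aggregated into a sample mean and variance", and the model is Y_ij ~ N(α_i + β_i x_ij, σ_i), with α_i ~ N(α_0, τ_α²) and β_i ~ N(β_0, τ_β²). The outcome "is the placebo subtracted UACR response for the" ith subject at time j. The covariate equals 1 "if treated with dapagliflozin; =0 if placebo treated". On priors the SAP says only "Again, we used non-informative prior for" the two means, the two variances and σ_i.

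The section does not say what a placebo-subtracted response is for a placebo record, what j indexes (cycle, period or day), or which parameter carries the 10/20/30% posterior probabilities. The analysis is then repeated for the secondary outcomes, and SAP 5.2 runs six subgroup analyses "by adding a subgroup parameter to the Bayesian hierarchical model as described above".

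The frequentist model in the same section subtracts placebo once, inside the model: "Appropriate contrasts will be implemented to assess the placebo subtracted response during the first and second cycle".

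**The concern.** A placebo-subtracted response already uses both treatments, so it has no treatment label of its own. Regressing it on a treatment indicator leaves the model without a contrast to estimate, unless the analyst invents a value for placebo records. The SAP does not make that choice, and different choices give different answers.

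Two things are at stake. The first is the population-level posterior probability of a clinically meaningful response. The second is τ_β, the between-patient spread of the response. The protocol's rationale (Summary and section 1) is to tell true variation in drug response from random variation, so a model that cannot identify τ_β, or that inflates it, bears directly on the trial's own question.

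**Working it through.** **The plan's own figure.** The only design figure is >80% power with 20 patients for a correlation of 0.6 at alpha 0.05 (SAP 3.2). Fisher z: atanh(0.6)·√17 - 1.960 = 0.693 × 4.123 - 1.960 = 0.898, so two-sided power is 81.5%. It reproduces, and it does not depend on the Bayesian model.

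**Inputs.** From the documents: 20 patients, two cycles of two periods, and an illustrative effect of -36.2% (protocol 6.3, a prior trial with 24-hour albumin excretion), i.e. ln(0.638) = -0.449. Assumed, because the documents give no values: between-patient SD of the effect τ = 0.20 and residual SD of a period-level log change s = 0.30. D and P denote a patient's log changes on dapagliflozin and placebo.

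**(a) Y as the SAP builds it: Y = D - P, one per cycle.**
- Both records of a patient have x = 1. The design matrix [1, x] has rank 1 for two parameters. The likelihood contains α_i + β_i only, and the variances enter only as τ_α² + τ_β².
- The sum α_0 + β_0 is well estimated: variance τ²/20 + 2s²/40 = 0.0020 + 0.0045 = 0.0065, SD 0.081, centre -0.449.
- With independent N(0, S²) priors on α_0 and β_0 and the variances taken as known, the data say nothing about α_0 - β_0. So β_0 has posterior mean of about -0.449/2 = -0.225 and SD of about S/√2: 0.71, 7.1 and 70.7 for S = 1, 10 and 100.
- Response probabilities for S = 10. The log thresholds for 10%, 20% and 30% reductions are -0.105, -0.223 and -0.357. From β_0: Φ(0.120/7.07), Φ(-0.002/7.07) and Φ(-0.132/7.07), that is 0.51, 0.50 and 0.49. From α_0 + β_0: Φ(0.344/0.081), Φ(0.226/0.081) and Φ(0.092/0.081), that is above 0.99, above 0.99 and 0.87.

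**(b) Dapagliflozin records subtracted, placebo records left raw.** β estimates (D - P) - P = D - 2P. On the ratio scale the true 0.638 is divided once more by the placebo ratio. An assumed placebo change of -10% gives 0.638/0.90 = 0.709 (-29.1%); +10% gives 0.638/1.10 = 0.580 (-42.0%). The bias vanishes only if placebo does nothing. The documents give no placebo change.

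**(c) All records centred on the patient's own placebo mean.**
- The mean of β is right: D minus mean P, against placebo records averaging zero.
- The placebo records of every patient now average exactly zero, so τ_α is estimated as zero. Pooling σ across patients, the dapagliflozin records give sum of squares s² on 1 df and the placebo records give s² spread over 2 df, so the residual variance is 2s²/3 instead of s².
- The patient effect has variance τ² + s², and the model assigns only (2s²/3)/2 = s²/3 of it to error. The rest goes to τ_β² = τ² + 2s²/3.
- At s = 0.30: √(0.04 + 0.06) = 0.32 against a true 0.20, and √0.06 = 0.24 when there is no true variation at all. With τ = 0.20, s = 0.20 gives √(0.04 + 0.0267) = 0.26 and s = 0.40 gives √(0.04 + 0.1067) = 0.38.
- The population interval is not too narrow. The true SD of the mean effect is √((0.04 + 0.09)/20) = 0.081. The model gives √((0.10 + 0.03)/20) = 0.081, or √(0.0065 + 0.06/40) = 0.089 if α_0 is estimated too.

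**(d) Y as the un-subtracted period-level change.** Each patient has x = (1, 0, 1, 0) in some order, so the rank is 2. Simulated group-mean β (2,000 trials of 20 patients) was -0.449, -0.446 and -0.449 for placebo changes of 0, -10% and +10%, against a true -0.449.

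**The case against.** The strongest reply is that this is a wording slip. SAP 5.1 itself defines the period-level change log(UACR_end/UACR_baseline). A patient intercept, a patient slope and a 1/0 indicator make sense with that outcome, and the frequentist model has the same structure. Striking the words for placebo subtraction makes the model executable. That is plausible, and it is the fix proposed here. But the text is legible, nothing elsewhere corrects it, and the SAP's own construction of the response leads to (a).

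Several stronger readings are tempting and should not be drawn:
- That the treatment effect cannot be estimated at all. Under (a), α_0 + β_0 is still the placebo-subtracted effect and is stable; what is lost is β_0 and the variance split.
- That β_0 has no proper posterior. This needs flat improper priors; the SAP says only non-informative. With diffuse proper priors the posterior exists but merely reflects the prior.
- That the effect must be either unidentified or doubly subtracted. Reading (c) is neither.
- That intervals are about 29% too narrow (√½ = 0.71 against 1.00). Under (c) this holds for a single patient's estimate with known error SD and α_i = 0. It does not hold for the population interval.
- That the trial's analysis as a whole fails. The patient-level Bayesian step is separate, the mixed models are unaffected, and protocol 10.1 describes only mixed-model analysis of the primary parameter.

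**Conclusion.** The model is wrong as written and has to be corrected before it is run. With the response built as the SAP describes, β_0 and the division between τ_α² and τ_β² are set by the prior, and the target parameter for the 10/20/30% probabilities is not named. In the illustration, the choice of parameter moves the probability of a 30% reduction from about 0.49 to 0.87. The undescribed alternatives either bias the mean effect by an amount that depends on the placebo change, or turn placebo noise into apparent response heterogeneity (0.24 where the truth is zero).

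The identification result in (a) and the form D - 2P in (b) are algebra and need no assumed values. The magnitudes rest on the assumed SDs, the borrowed -36.2%, the assumed placebo changes of ±10%, and, in (c), a residual SD pooled across patients where the SAP writes σ_i.

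Affected: the population-level posterior probabilities for UACR, their repeat for the secondary outcomes, and the six subgroup analyses. Not affected: the frequentist and heterogeneity models in SAP 5.1, and the sample size.

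**What to change.** In SAP 5.1, define Y_ij as the un-subtracted log(UACR_end/UACR_baseline) of patient i in treatment period j (four per patient). Keep x_ij as coded. State that β_i and β_0 are the placebo-adjusted responses for the patient and the population, and that the 10/20/30% probabilities are computed on them. Define the secondary outcomes in the same way. In SAP 5.2, say that the subgroup term acts on β.

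An equivalent repair keeps the per-cycle difference as Y and drops the indicator: Y_ij ~ N(β_i, σ_i), with β_i ~ N(β_0, τ_β²).

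The cost is one sentence and, for the second option, one formula. Data collection, sample size and the frequentist models do not change. A cycle or period term to match the mixed models, and proper weakly informative priors on the SDs, could be added at the same time, but the correction does not need them.
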